2.2 Secondary Objectives

Secondary objectives are to determine whether combined CCNU/TMZ/RT therapy is superior to standard TMZ/RT therapy regarding progression-free survival and time to treatment failure as well as to determine acute and late toxicity of CCNU/TMZ therapy including its effects such as the delay of subsequent courses due to acute toxicity.

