4. TRIAL DESIGN

This is a multicenter, randomized, open-label phase III trial for newly diagnosed glioblastoma patients with methylated MGMT promoter in their tumor. The study includes the following steps:

Screening phase (1-3 weeks after resection): Patients with previously untreated GBM are screened for the trial. After obtaining informed consent for determination of MGMT promoter methylation status and reference neuropathology, a block of paraffin-embedded tissue is sent for reference neuropathology review to the Department of Neuropathology, University of Bonn. From there, tissue is sent to MDxHealth, where the MGMT promoter methylation status is determined by methylation-specific PCR.

Baseline and randomization phase (week 3-5 after resection): Baseline examinations are performed. After obtaining the MGMT promoter status and confirmation of GBM histology (for the form to submit reference neuropathology and MGMT testing see appendix 3) and obtaining informed consent for trial participation, inclusion/exclusion criteria are evaluated and documented, patients are randomized for standard TMZ chemotherapy or experimental CCNU/TMZ therapy, both in combination with standard RT. Therapy (i.e. RT) has to start within 2 weeks after randomization and 5 weeks after surgery. A 5 week interval is generally accepted for clinical trials in GBM and does not impair therapeutic efficacy (Blumenthal et al., 2008).

Treatment phase: The treatment phase as well as the follow-up phase of the trial is summarized in figure 1. The treatment phase should start not later than 5 weeks after surgery and not later than 2 weeks after randomization and baseline visit.

[figure not shown]
The trial includes two treatment arms:

Experimental arm (CCNU/TMZ arm; 50% of patients): the first course of CCNU (100 mg/m² day 1) and TMZ (100 mg/m²/day, day 2-6) is started on the first day of RT (60 Gy in 2 Gy fractions, 5 days/week). The following 5 courses are applied 6 weeks after the start of the previous course. In the experimental arm, not more than 6 six week courses can be applied.

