5.1.3.1 Dose modifications of CCNU/TMZ

Dosing is based on adverse event (AEs) during the prior treatment cycle. If a patient experiences several adverse events, the recommended dose adjustment is to be based on the toxicity that requires the greatest dose reduction. Dose adjustments are to be made according to the system showing the greatest degree of toxicity. Adverse events will be graded using the NCI Common Terminology Criteria for Adverse Events Version

4.0 (CTCAE). In response to acute toxicity, the dosage of TMZ will be reduced according to the criteria outlined in this section. In any case of hematologic toxicity of grades 3 or 4, it is recommended to obtain RBC, platelets, WBC and a differential blood count at least twice weekly. Leucocytes, ANC and platelets have to be determined at least 7 days after the last G-CSF application or transfusion of platelets.

As in the previous phase II trial, the doses of CCNU and TMZ are individually adjusted in following courses according to white blood cell (WBC) and platelet nadirs during the previous course according to the following scheme:

- In case the nadir (WBC < 1500/ μ l or thrombocytes < 50000/ μ l) occurred after day 25, CCNU will be reduced by one dose level with the dose levels being 100%, 75% and 50% of the initial dose. In case of WBC <1500/ μ l thrombocytes <50000/ μ l at the dose level of 50%, CCNU has to be permanently discontinued.
- Depending on the nadirs during the first 25 days of the previous course TMZ will be decreased to the lower dose levels of 75 mg/m² or 50 mg/m² or increased stepwise to the higher dose levels of 120 mg/m², 150 mg/m² and 200 mg/m² according to the following schedule:
 - reduction by 1 dose level if WBC <1500/ μ l or platelets < 50 000/ μ l;
 - reduction by 2 dose levels if WBC <1000/ μ l or platelets < 25 000/ μ l;
 - increase by 1 dose level if RT was completed and WBC >2500/ μ l and platelets >100000/ μ l.
 - In case of WBC <1500/ μ l or thrombocytes <50000/ μ l at the lowest dose level of 50 mg/m², TMZ has to be permanently discontinued.
- In case of any non-hematological toxicity CTCAE grade 3/4, the substance causing the toxicity will be withheld in further courses and therapy within the trail may continue with the substance not causing the toxicity.

Using this scheme, the individual dose adaptation in subsequent courses allows to apply the individually highest possible dose of chemotherapy which may differ greatly between different patients.

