6.2.2 Definition and evaluation of efficacy endpoints

Overall survival (Primary endpoint): Survival is defined as the duration from randomization to the date of death due to any cause.

Progression-free survival: The progression-free survival is defined as the time from randomization to the first documented evidence of progression of disease according to the modified RANO criteria.

Overall Response: The overall response rate is defined as the relative proportion of patients with complete and partial responses.

Time to Treatment Failure: Time to treatment failure is defined as the duration from the day of diagnosis (surgery obtaining histology) to any of the following:

- Death for any reason
- relapse or progressive disease (PD) during or after study treatment,
- discontinuation of combined CCNU/TMZ treatment for any reason before the completion of 3 cycles CCNU/TMZ

Frequency of delay of the next CCNU/TMZ or TMZ course by more than 2 weeks

Quality of Life: The EORTC QoL questionnaire modules QLQ-C30 and BN20 will be used to assess the quality of life. These assessments will be performed on the visits specified in the Time and Events Schedule. Patients will be given these questionnaires to complete by a study center staff member. The staff member will collect each completed assessment and check it for completeness before giving the patient the next assessment to complete.

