9.3 Statistical and Analytical Methods: Efficacy parameters

Statistical analysis starts 36 months after the inclusion of the last patient. Statistical analysis will be performed at the Institute of Medical Biometry, Informatics and Epidemiology (IMBIE) at the University of Bonn Medical Center (Dir.: [name]. [name]). OS, the primary parameter, will be compared between treatment groups using a two-sided log-rank-test at a level of 5% stratified for center and for RPA class. Centers contributing less than 3 patients for one arm of the treatment arms are pooled in this analysis. The primary confirmatory analysis will be based on the intention-to-treat (ITT) population. The ITT population contains all patients who have received a first dose

of chemotherapy (CCNU in the experimental arm and TMZ in the standard arm). Dropouts will be evaluated as censored observations at the time of dropout. An additional comparison will be made based on the per protocol population. The results of both analyses should be consistent. The per-protocol analysis includes all patients who have received two courses of CCNU/TMZ in the experimental arm or concomitant TMZ plus one course of adjuvant TMZ in the standard arm. Additionally, an analysis of the “as randomized” population will be performed.

The following secondary efficacy endpoints are also determined:

- Progression-free survival (PFS) determined by MRI (modified RANO criteria)
- Best response rate determined by MRI (modified RANO criteria)
- Frequency of delay of the next CCNU/TMZ or TMZ course by more than 2 weeks
- Acute toxicity during radiotherapy and chemotherapy according to CTC AE V4.0
- Quality of life, determined by EORTC QLQ questionnaires
- Evaluation of late neurotoxicity by MMSE and NOA-07 test battery

Survival parameters are measured in days starting from the day of start of treatment (first day of RT). Surviving patients and patients lost for follow-up are censored for the Kaplan-Meier analysis. Overall survival and progression-free survival will be summarized by Kaplan-Meier curves. Median time estimates as well as associated 95% confidence intervals will be reported. In addition Cox regression analyses adjusted and unadjusted for stratification factors such as age, performance score, extent of resection will be performed in an exploratory manner. The analysis will be based on the intent-to-treat population and repeated for the per-protocol population.

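### Time to treatment failure counts early discontinuation only in the CCNU/TMZ arm, so the planned superiority comparison on this secondary endpoint is tilted against that arm

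*Protocol*

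**What the plan says.** Section 2.2 of the protocol aims to show that CCNU/TMZ is "superior to standard TMZ/RT therapy regarding progression-free survival and time to treatment failure", and section 2.3 lists TTF among the secondary endpoints.

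The definition is in section 6.2.2: "Time to treatment failure is defined as the duration from the day of diagnosis (surgery obtaining histology) to any of the following". Three events follow. Death and relapse or progression apply to everyone. The third is "discontinuation of combined CCNU/TMZ treatment for any reason before the completion of 3 cycles CCNU/TMZ". No standard-arm counterpart is given.

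Stopping of treatment is foreseen in both arms. Section 3.5 lists reasons that apply to any patient, and section 5.1.4 has its own TMZ discontinuation rules. In the experimental arm, section 5.1.3.1 provides that after grade 3/4 non-hematological toxicity "therapy within the trail may continue with the substance not causing the toxicity".

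Three time origins appear:
- TTF starts at surgery.
- PFS starts at randomization: "The progression-free survival is defined as the time from randomization to the first documented evidence of progression of disease". OS does too.
- Section 9.3 states: "Survival parameters are measured in days starting from the day of start of treatment (first day of RT".

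TTF is missing from the secondary endpoints in the synopsis and in section 9.3.

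**The concern.** A comparison between arms needs the same event definition in each. Here a standard-arm patient who stops TMZ for good early, without progression or death, has no TTF event. An experimental-arm patient who stops the combination at the same time has one. The experimental trigger is also wide: it is loss of the combination, for any reason, so a patient still on trial therapy with one agent counts as a failure. Treatment is open-label, so part of this event is at the discretion of patient and physician and is counted on one side only.

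At stake is whether one stated secondary objective can be answered. With equal progression and death, TTF would lean against CCNU/TMZ; with a true benefit, it would understate it.

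**Working it through.** **No plan figure to reproduce.** The protocol gives no assumption, test or power for TTF. The check is a reading of the event list, followed by an illustration of size.

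**Events side by side (section 6.2.2).**

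| Situation before week 18, no progression or death | CCNU/TMZ arm | TMZ arm |
|---|---|---|
| All study chemotherapy stopped for good | TTF event | not an event |
| One agent dropped, the other continued | TTF event | cannot occur |

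An additional event type in one arm can only shorten TTF in that arm. This fixes the direction.

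**Length of the window.** Three CCNU/TMZ courses: 3 x 42 / 7 = 18 weeks. In the standard arm the same point is reached after concomitant TMZ, the pause and two adjuvant courses: 6 + 4 + 2 x 4 = 18 weeks.

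**Inputs.**
- 64 patients per arm (section 9.1).
- Follow-up of 36 to 60 months: two years of recruitment plus three years (synopsis, section 9.1).
- Share q stopping the combination early. The only anchor is two grade 3/4 organ toxicities among 31 phase II patients (section 1.1): 2/31 = 6.5%. Their timing is not stated. Values of 10% and 20% are assumptions.
- Median time to progression or death of 15 months, equal in both arms (assumed). Medians of 7.9 months (section 1.1, unselected patients), 12 and 17 months were also tried.
- Unstratified log-rank test, two-sided 5%. The protocol states a log-rank test for OS only; its use here is an assumption.

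**Order of magnitude.** 64 x 2/31 = 4.1 experimental-arm patients would have the extra event. With stopping spread evenly over 18 weeks the mean is 9 weeks, or 9 x 12/52 = 2.1 months. The chance of having already progressed or died by then is 1 - 0.5^(2.1/15) = 9%. So nearly all of these four are failures that TTF would not otherwise have recorded so early.

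**Simulation.** Let X be the exponential time to progression or death. In a share q of the experimental arm, TTF = min(X, D) with D uniform over 0 to 18 weeks; otherwise TTF = X. The hazard ratio is exp((O - E)/V), and CCNU/TMZ is found worse when (O - E)/sqrt(V) > 1.96. There is no true effect, and the median is 15 months:

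| q | As written: HR; found worse | Event in both arms: HR; found worse | As written, early stoppers progress 3 times faster: HR; found worse |
|---|---|---|---|
| 6.5% | 1.07; 6% | 1.00; about 2.5% | 1.02; 3% |
| 10% | 1.11; 9% | 1.00; about 2.5% | 1.03; 4% |
| 20% | 1.25; 21% | 1.00; about 2.5% | 1.07; 6% |

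Across medians of 7.9, 12 and 17 months, with stopping independent of prognosis, the as-written hazard ratio is 1.06-1.07, 1.10-1.11 and 1.20-1.26 for the three values of q.

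**With a true benefit.** The 50% prolongation of PFS mentioned in section 1.2 corresponds to 1/1.5 = 0.667. At q = 6.5%, under independence and across the same three medians, the chance of showing superiority on TTF is 35-45% as written and 47-57% with the event counted in both arms. Without any discontinuation event it is 52-61%. Part of the loss therefore comes from having such an event at all, not from the asymmetry.

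**Time origin.** The protocol places the "Baseline and randomization phase (week 3-5 after resection", so TTF includes some weeks before allocation. Adding 3 to 5 weeks to every patient, with no discontinuation event, gives a hazard ratio of 1.00 and about 2.5% found worse. This time is balanced in expectation.

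**The case against.** The best defence is that the protocol has other treatment-failure rules. Sections 5.1.3 and 5.1.4 assume treatment failure when the next course is delayed by more than six weeks, in either arm, and section 5.1.1 has a similar rule for radiotherapy interruptions. A standard-arm patient who stops TMZ for good never starts the next course and could be called a failure on that basis. However, the list in 6.2.2 does not refer to these rules. Adding them to both arms would still leave the CCNU/TMZ-specific event in one arm only. What stands is that the protocol uses the term in two ways and should settle which one TTF means.

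The second defence concerns importance, and it largely stands. TTF is the last secondary endpoint in 2.3, has no stated test or error allocation, and is absent from 9.3. The bias works against the sponsor's hypothesis, so it cannot produce a false claim of superiority. PFS serves the same secondary objective and is unaffected.

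The third concerns size. The 20% row has no support in the protocol, and independence between stopping and prognosis is only an assumption. Stopping for any reason may include deteriorating patients who would soon progress anyway, and the effect then shrinks to the last column of the table.

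A reader might also infer that starting the clock at surgery contributes to the bias. It does not: surgery precedes allocation in both arms, and the check shows no shift.

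**Conclusion.** The definition is wrong as written. It gives the two arms different endpoints for a comparison the protocol itself plans, and an analysis plan that followed it would inherit the problem. The direction, against CCNU/TMZ, needs no assumption. The size does: about 1.07 on the hazard ratio scale and 6% instead of 2.5% at the only documented anchor, roughly 1.25 at an assumed 20% of early stoppers, and as little as 1.02 (at 6.5%) or 1.07 (at 20%) if those patients progress three times faster.

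It should be corrected, but it does not threaten the trial's main conclusion. The documents do not support a reading that CCNU/TMZ will be shown as significantly worse, since even at the anchor this happens in about one trial in seventeen (6%). Nor do they support a reading that OS or PFS is affected. The three time origins and the uneven listing of TTF are consistency faults that stand separately.

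**What to change.** 1. In 6.2.2, define the third event identically in both arms: permanent discontinuation of all study chemotherapy within the first 18 weeks of treatment (3 x 6 weeks of CCNU/TMZ, or 6 + 4 + 2 x 4 weeks of the TMZ schedule). Dropping one agent while continuing the other would then not be an event. Alternatively, delete the third event in both arms.
2. Start TTF at randomization, as 6.2.2 does for OS and PFS, and bring the time origin in 9.3 into line with 2.3 and 6.2.2.
3. State whether the delay rules in 5.1.1, 5.1.3 and 5.1.4 count as TTF events; if so, count them in both arms.
4. List TTF consistently in the synopsis, 2.3 and 9.3.

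Only endpoint wording changes; treatment and sample size do not. The sponsor should confirm that the case report form records when each drug was stopped in both arms, as the protocol does not say this expressly. The change should be made before anyone sees outcomes by arm, so that it cannot appear data-driven.

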6.3 Safety Evaluations

Safety is monitored continuously throughout the trial as detailed in Table 2 “Time and Schedule of Events”. The study will include the following evaluations of safety and tolerability:

Adverse Events: Adverse events will be reported throughout the study at each visit. Adverse events will be followed by the investigator.

Clinical Laboratory Tests: Laboratory tests at each visit will be performed at the Laboratory of the treating University Medical Center. Between visits, weekly laboratory testings are performed by the general practitioner or oncologist of the patients and results are to be faxed within 24 hours to the local investigator. All laboratory reports will be reviewed by the investigator. This review must be documented, and any clinically relevant changes occurring during the study must be recorded in the adverse event section of the CRF.

Vital Signs

Physical and neurologic examination: Any clinically significant abnormalities persisting at the end of the study will be followed by the investigator until resolution or until reaching a clinically stable endpoint.

Karnofsky performance score: Karnofsky performance score is outlined in appendix 1

NOA-07 test battery: the NOA_07 test battery is outlined in section 9.2.7.

MMST: The MMST is outlined in appendix 2

General safety monitoring: The management of SAE within the study group will be according to ICH GCP, i.e. depending on the criteria expected/unexpected, suspected/

not suspected, dead/alive SAEs have to be announced to the sponsor within the legal time frame. Similarly, the sponsor will announce SAEs to the authorities within the legal time frame. For details see chapter 7 (adverse event reporting). Safety is independently monitored by the Data monitoring and safety board as detailed below.

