Adverse events in man mainly affect the hematopoietic system with thrombocytopenia, leucocytopenia and anaemia. Myelosuppression occurs delayed, mainly after 4-6 weeks and can be cumulative. Further, medication with CCNU might lead to nausea and vomiting, more rarely to diarrhea. Occasionally, moderate hepatic dysfunction has been observed. In rare cases, pulmonary fibrosis, alopecia, stomatitis and minor neurological dysfunctions, e.g. apathia, ataxia and desorientation. In a few cases, irreversible damage of the optic nerve has been described in the combination with radiotherapy. CCNU can have carcinogenic, mutagenic and teratogenic effects.

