5.1.3 Experimental arm: chemotherapy with CCNU/TMZ

The experimental arm consists of six 42 day-courses of CCNU 100 mg/m²/day (day 1) and TMZ 100 mg/m²/day (day 2-6). The first course starts with the first day of RT. CCNU and TMZ are applied orally. TMZ and CCNU have to be taken on empty stomach meaning at least 2-3h hours after the last meal. At least 30 minutes earlier, a serotonin antagonist such as ondansetron or tropisetron have to be taken as antiemetic. TMZ and CCNU is applied on an outpatient base. The doses of CCNU and TMZ are justified by the previously published phase II trial ([name] et al., 2006; Glas et al., 2009) which used the same doses and which provided the promising results that are the base for the present trial. The next course of CCNU/TMZ can only be started if WBC are >3000/μl, neutrophil counts are >1500/μl and platelets are >100000/μl and in case CTC grade < 2 toxicity. Treatment failure is assumed in case of a delay of more than 6 weeks for the start of the next course of CCNU/TMZ. After progression or treatment failure of a patient the further therapy is applied at the discretion of the treating physician.

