6. CLINICAL EVALUATION, LABORATORY TESTS, FOLLOW-UP

6.1 Study procedures

The attached Time and Events Schedule (Table 2) summarizes the frequency and timing of the various investigations and safety measurements. The neuroradiologic evaluation of response must be performed by contrast-enhanced MRI. A deviation of more than 5 days regarding the defined timepoints for each visit is regarded as a

protocol violation. This does not apply to the delay of chemotherapy courses due to prolonged toxicity in the previous course. The therapeutic options for patients who progress during study treatment are not determined by this protocol, but according to our previous experiences ([name] et al., 2006), intensified TMZ chemotherapy according to the one week on/off schedule (Wick et al., 2007) is recommended. To ensure reproducibility of MRI evaluation, all MRIs have to be reviewed by the reference neuroradiologist [name]. [name], Division of Neuroradiology, Department of Radiology, [name]. The MRIs have to be sent blinded (only labelled with Pat.-ID) to the reference neuroradiologist to ensure unbiased progression assessment.

In particular, the study visits include the following items:

- **Screening visit (week 1-3 after resection):**
 - Written informed consent for neuropathology reference testing and for MGMT testing

- **Baseline visit (week 3 to 5 after resection):**
 - Written informed consent for the trial
 - Inclusion/exclusion criteria (including MGMT and reference neuropathology test result)
 - Medical history and demographics
 - Vital signs
 - physical and neurological examination
 - concomitant medication
 - Karnofsky PS
 - Mini-Mental-Status evaluation and neurocognitive testing (NOA-07 test battery)
 - quality of life questionnaire
 - baseline contrast enhanced MRI scan (all post surgery MRIs not older than 3 weeks can be taken as baseline MRI (ideally early post surgery (72h))
 - ECG
 - spirometry
 - pregnancy test for women with reproductive potential
 - complete blood count and CRP
 - Blood sampling for translational studies

- serum chemistry and urine analysis
 - coagulation
 - Documentation of preexisting conditions in analogy to CTCAE
 - Randomisation
- **At the beginning of each course of CCNU/TMZ or TMZ:**

(Standard arm (TMZ): visit can be done within 5 days before start of cycle;
Experimental arm (CCNU/TMZ): visit has to be done on day of cycle start.

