Before start of chemotherapy (concomitant TMZ or first cycle CCNU/TMZ: blood analysis obtained in Baseline can be used if not longer than 5 days old)

 - Assessment of survival
 - vital signs,
 - physical and neurological examination,
 - concomitant medication,
 - Karnofsky PS,
 - complete blood count and CRP,
 - serum chemistry and urine analysis,
 - coagulation,
 - CTCAE evaluation

Throughout all treatment courses of TMZ and CCNU/TMZ starting with radiotherapy a differential blood count has to be determined weekly by the general practitioner of each patient. The results have to be faxed within 24 hours to the treating center for review. In case pathological laboratory values are regarded by the local investigator to have medical consequences (e.g. grade 4 neutropenia requiring prophylactic antibiotic treatment) the differential blood count has to be repeated at the study center.

- **MRI/ progression assessment visits every 12 weeks (+/- 5 days) after randomization during study treatment and follow up until end of study**
- (Follow-up of all patients ends 36 months after the inclusion of the last patient. All patients in the trial are followed until this time point.)
 - vital signs
 - physical and neurological examination

- concomitant medication (all medication during the treatment phase, during follow-up this includes only the tumor-related medication)
- further tumor-directed therapy (surgery, radiotherapy, chemotherapy): day of start of further therapy, day of progression for each therapy
- Karnofsky PS
- Mini-Mental-Status evaluation
- quality of life questionnaire
- contrast-enhanced MRI scan
- NOA-07 test battery (only every 24 weeks)
- complete blood count and CRP
- Blood sampling for translational studies
- serum chemistry and urine analysis
- coagulation
- CTCAE evaluation
- Assessment of progression/survival

Table 2: Schedule of Study procedures

	Screening visit Week 1-3	Baseline visit Week 3-5 ⁽²⁾	Treatment phase		After 6 courses of CCNU/TMZ or TMZ
			At the beginning of each course of CCNU/TMZ or TMZ	MRI/progression assessment visit every 12 weeks ⁽¹⁾	MRI/progression assessment visit every 12 weeks ⁽¹⁾
Clinical examination					
Informed consent for MGMT and reference neuropathology ⁽³⁾⁽³⁾	x				
Informed Consent for trial participation		x			
Results of MGMT testing and ref. neuropathology		x			
I / E criteria, demographics and medical history		x			
Evaluation of preexisting conditions in analogy to CTCAE		x			

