9.4 Safety Analysis

Patients who did not receive at least one dose of any study medication will be excluded from the analysis of safety. Tables of adverse event incidence (preferred term classification) and individual incidence will be produced. A complementary analysis of adverse events by severity of event and by relationship to trial treatment will also be performed. Dose reductions, delay of therapy in subsequent courses ("Frequency of

delay of the next CCNU/TMZ or TMZ course by more than 2 weeks” as secondary endpoint) and premature withdrawals will also be described.

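### Section 6.3 ties adverse event entry of laboratory changes to judged clinical relevance, 7.1.1 and 7.2.1 do not, and the weekly counts have no specific route into the CRF

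*Protocol*

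**What the plan says.** Three places in the Protocol decide whether a low blood count becomes a recorded adverse event.

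- Section 6.3: "All laboratory reports will be reviewed by the investigator", the review is documented, and "any clinically relevant changes occurring during the study must be recorded in the adverse event section of the CRF". No CTCAE grade or numerical limit is attached.
- Section 7.1.1 includes laboratory test abnormalities in the definition of an adverse event, without a relevance condition.
- Section 7.2.1 requires all adverse events in the source document and the CRF, irrespective of seriousness, severity or presumed relationship.

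On the counts themselves, 6.1 requires a weekly differential blood count outside the center in both arms, from the start of radiotherapy: "The results have to be faxed within 24 hours to the treating center for review". Table 2 lists blood counts at baseline, at course start and at the 12-weekly visits, but not the weekly ones. Section 12.2 says in general terms that all study data go into the CRF.

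Sections 2.3 and 9.3 name acute toxicity by CTCAE v4.0 as a secondary endpoint. Section 9.2 states that patients and treating physicians cannot be blinded.

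**The concern.** CTCAE grades for cytopenia follow from the count. A rule that first asks whether a change is relevant puts a judgement ahead of the grade, and here an unblinded investigator makes that judgement. Myelosuppression is the main expected extra harm of CCNU/TMZ: 1.1 and 1.3 report high-grade myelotoxicity in 42% of the phase II patients. Section 1.2 makes a change of practice conditional on acceptable acute toxicity. If centers or arms apply the relevance test differently, the comparison behind that conclusion is partly one of recording habits.

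The weekly values matter most here. For CCNU, 1.4.2 says "Myelosuppression occurs delayed, mainly after 4-6 weeks and can be cumulative". Course-start visits in the experimental arm fall on a day when counts have to be above set limits, so those visits alone would show little of the nadir.

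**Working it through.** There is no stated figure to reproduce. The check compares the recording rules and then asks whether the nadirs are measured at all.

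**1. Recording rules applied to one case.** Take a patient without symptoms whose platelets fall between visits and recover before the next course.
- Under 6.3, entry is required only if the investigator calls the change relevant; otherwise that section is silent.
- Under 7.1.1 with 7.2.1, the abnormality is an adverse event and is recorded whatever its severity.
- Section 7.1.2 describes intensity as mild, moderate or severe, so an entry in that form does not by itself carry a CTCAE grade.

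A site can follow 6.3 and omit the event, or follow 7.2.1 and enter it.

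**2. Course-start visits.**
- Experimental arm (6.1): "Experimental arm (CCNU/TMZ): visit has to be done on day of cycle start". Section 5.1.3: "The next course of CCNU/TMZ can only be started if WBC are" above 3000/µl, neutrophils above 1500/µl and platelets above 100000/µl. A count on the actual start day of courses 2 to 6 is therefore a recovered count.
- Standard arm (6.1): "visit can be done within 5 days before start of cycle".

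**3. Weekly counts in a 42-day course.** If the weekly draw first falls on day d (1 to 7), draws fall on d, d+7, …, d+35, which is 6 draws.
- After day 25: d+28 and d+35 always qualify, and d+21 also qualifies when d is 5 to 7. That gives 2 draws for d = 1 to 4 and 3 for d = 5 to 7.
- Days 28 to 42: 2 draws for d = 1 to 6, and 3 for d = 7 (days 28, 35 and 42).

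The late window is sampled in every course.

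**4. The 12-weekly visits.** These run from randomization and include a blood count and CTCAE evaluation. Treatment starts 0 to 2 weeks after randomization (section 4). Visits at weeks 12, 24 and 36 therefore fall 10–12, 22–24 and 34–36 weeks after treatment start. With 6-week courses and no delay, courses 2, 4 and 6 begin 6, 18 and 30 weeks after treatment start. Subtracting gives weeks 4 to 6 of courses 2, 4 and 6, before the ±5-day window.

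**5. Use of the nadirs.** Section 5.1.3.1 bases dose changes in the experimental arm on the nadirs of the previous course, before and after day 25, so the center has to look at them.

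**6. Scale, for context only.** At the phase II rate, 0.42 × 64 = 26.9, or about 27 patients in the experimental arm with high-grade myelotoxicity. The Protocol does not say how many such events would be judged not relevant.

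**The case against.** The best defence is that 6.3 sets a minimum. It says relevant changes must be entered; it does not say others may be left out. On that reading 7.2.1 is the general rule and 12.2 covers the weekly values. The Protocol also ties action to severe cytopenia: more frequent counts and dose steps in 5.1.3.1, and prophylaxis in 5.3.2. Values that trigger such action are hard to call irrelevant. Adverse events are also collected by questionnaire for each course (Synopsis), so they are not limited to the visit day.

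Much of this stands, and it rules out several stronger readings that a reader might infer:

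- **That laboratory toxicity reaches the CRF solely through the relevance judgement.** Sections 7.1.1 and 7.2.1 say otherwise; the defect is an unresolved conflict.
- **That delayed nadirs are missed because course visits follow recovery.** The weekly counts and 12-weekly visits cover the late window.
- **That the experimental arm will look too safe.** Weekly sampling and the recording rule are the same in both arms. The recording rule can produce a difference between arms only through unblinded judgement, and extra vigilance for CCNU could raise reporting just as well.
- **That a given share of the 42% would go unreported.** Any such share would be a bare assumption.
- **That 9.4 is deficient.** It says "Tables of adverse event incidence (preferred term classification) and individual incidence will be produced" and adds severity, relationship, dose reductions, delays and withdrawals. A worst-grade table may sit in the statistical analysis plan, which is not shown.

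The defence does not remove the conflict itself. The sentence on laboratory reports in 6.3 still carries an ungraded criterion, and the Protocol does not say that 7.2.1 overrides it. Nor can a statistical analysis plan recover weekly values that were never transcribed.

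**Conclusion.** The point holds as a conflict between recording rules, together with an unspecified data route. Section 6.3 is at odds with 7.1.1 and 7.2.1, and beyond the general sentence in 12.2 nothing says that the weekly values enter the CRF. Hematological toxicity within the CTCAE v4.0 secondary endpoint can therefore be recorded differently between centers or arms.

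Neither the size nor the direction of any distortion can be derived from the documents. Severe cytopenia that prompts action is likely to be recorded. Transient, silent low counts between visits are the more exposed. The primary endpoint, overall survival, is untouched. The conclusion assumes that sites read 6.3 as the operative rule for laboratory reports at least some of the time, and that the CRF has no dedicated field for weekly values; the CRF is not among the documents. This is an improvement worth making, not a flaw that undermines the trial.

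**What to change.** 1. Reconcile 6.3, 7.1.1 and 7.2.1 into a single rule for recording laboratory abnormalities.
2. State that hematological CTCAE v4.0 grades in both arms are derived from the lowest WBC, neutrophil, platelet and haemoglobin value per course, weekly counts included, independent of judged relevance. Count the concomitant phase of the standard arm as one course, and say where counts from the 4-week pause belong.
3. Require these lowest values to be transcribed to the CRF, and list the weekly counts in Table 2.

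The cost is wording plus data entry: 4 values × 6 courses = 24 per patient in the experimental arm, and 4 × (1 + 6) = 28 in the standard arm, at most. The centers already receive the weekly reports; this assumes that the reports include haemoglobin.

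One caution for the analysis: a 42-day course holds 42/7 = 6 weekly counts and a 28-day course 28/7 = 4, so a worst value per course is not like for like between arms. The worst grade per patient over the treatment period is the fairer comparison. No dose or clinical rule changes.
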